2. STUDY OBJECTIVES

2.1. Primary

To evaluate the anti-tumor activity of MEDI0457 in combination with durvalumab.

2.2. Secondary

The secondary objectives are as follows:

- To determine the safety profile of MEDI0457 in combination with durvalumab in patients with recurrent/metastatic HPV 16- or 18- associated cancer,
- To evaluate the PFS and OS of patients with recurrent/metastatic incurable HPV-16/18 positive solid malignancies receiving the combination of MEDI0457 and durvalumab,

Version Number: 1.8 Date: July 26, 2019 Proprietary of MD Anderson Cancer Center

• To evaluate ORR by immune-related criteria of the combination of MEDI0457 and durvalumab in patients with recurrent/metastatic incurable HPV-16/18 positive solid malignancies, and

• To evaluate the disease control rate at 24 weeks.

2.3. Exploratory

The exploratory objectives are as follows:

- To determine the cellular and humoral immune response to immunotherapy with MEDI0457 in combination with durvalumab,
- To examine the correlation between anti-tumor activity and biomarkers including:
 - o HPV-specific cellular and humoral responses
 - o programmed death ligand 1 status
 - o the number of tumor infiltrating lymphocytes
 - o HPV 16/18 E6/E7 DNA levels and HPV 16/18 E6/E7 DNA sequence in biopsy tissue and plasma.
- To evaluate the pharmacokinetics and anti-drug antibodies (ADA) for durvalumab.

3. SUBJECT SELECTION AND PARTICIPATION

Each patient should meet all of the inclusion criteria and none of the exclusion criteria for this study.

Patients who fail to meet the eligibility criteria should not be enrolled or receive study medication. Patients who are enrolled but subsequently found not to meet all the eligibility criteria must not be initiated on treatment and must be withdrawn from the study.

Where a patient does not meet all the eligibility criteria but is incorrectly started on-treatment, the investigator should discuss with the supporting company and the IND sponsor (MDACC IND Office) to determine whether to continue or discontinue the patient from treatment.

3.1. Inclusion Criteria

For inclusion in the study patients should fulfill the following criteria.

- 1. Written informed consent in accordance with institutional guidelines.
- 2. Male and female patients age 18 years or older who are able and willing to comply with all study procedures.
- 3. For patients who are not HIV positive, cervical, anal, penile, vulvar, or vaginal cancer positive for HPV-16 and/or HPV-18 by the institutionally approved assay. For patients who are HIV positive, histologically or cytologically confirmed diagnosis of cancer at any site that is positive for HPV-16 and/or HPV-18 by the institutionally approved assay. Tumors may be positive for more than 1 HPV subtype as long as HPV-16 and/or HPV-18

Version Number: 1.8

Proprietary of MD Anderson Cancer Center Date: July 26, 2019

is present. Note: For the first 3 patients, only cervical, vulvar, or vaginal cancers will be enrolled.

- 4. Patients with cancer that is refractory to standard therapy, that have either relapsed after standard therapy or has no standard therapy that increases survival by at least three months, and/or that are not curable by salvage approaches including resection and/or reirradiation.
- 5. Has measurable disease, defined as at least one lesion that can be accurately measured in at least one dimension (longest diameter to be recorded) with a minimum size of 10 mm by computed tomography (CT) scan, except lymph nodes which must have minimum short axis size of 15 mm (CT scan slice thickness no greater than 5 mm in both cases). Indicator lesions must not have been previously treated with surgery, radiation therapy, or radiofrequency ablation unless there is documented RECIST v1.1 progression in the lesion after such therapy.
- 6. All patients must consent to pre-treatment biopsy of the tumor if it can be done safely (as judged by the investigator) during screening. Week 10 on-treatment biopsies will be required for a minimum 10 patients. After 10 paired biopsies have been obtained then Week 10 on-treatment biopsy will be made optional.
- 7. World Health Organization (WHO)/Eastern Cooperative Oncology Group (ECOG) performance status of 0 or 1.
- 8. Adequate organ and bone marrow function within 28 days of Day 0. Criteria "a" to "c" cannot be met with recent (within 28 days of screening test except as noted below) blood transfusions or require ongoing growth factor support:
 - a. Hemoglobin ≥ 9 g/dL (**Note:** No Transfusion within 7 days of beginning study treatment. Ongoing growth factor support is acceptable if on a stable dose for the past 56 days.),
 - b. Absolute neutrophil count $\geq 1,000/\text{mm}^3$,
 - c. Platelet count $\geq 100,000/\text{mm}^3$ and no transfusion in prior 4 weeks,
 - d. Total bilirubin (TBL) $\leq 1.5 \times \text{upper limit of normal (ULN)}$ except patients with documented Gilbert's syndrome ($> 3 \times ULN$),
 - e. Alanine aminotransferase (ALT) and aspartate aminotransferase (AST) $\leq 3 \times ULN$,
 - f. Serum creatinine < 2.0 mg/dL or creatinine clearance > 40 mL/min (measured or calculated according to the method of Cockcroft and Gault), and
 - g. For HIV+ patients: Documented HIV-1 infection with CD4 count > 200 cells/mm3 and viral load < 75 copies/mL.

3.2. **Exclusion Criteria**

Patients should not enter the study if any of the following exclusion criteria are fulfilled.

1. Any concurrent chemotherapy, IP, biologic, or hormonal therapy for cancer treatment; receipt of any investigational or approved anticancer therapy (chemotherapy, targeted

Version Number: 1.8 Date: July 26, 2019

Proprietary of MD Anderson Cancer Center

therapy, biologic therapy, monoclonal antibodies, etc.) within 21 days or 5 half-lives, whichever is shorter, prior to the first dose of MEDI0457; concurrent enrollment in another clinical study, unless it is an observational (non-interventional) clinical study or during the follow-up period of an interventional study.

- 2. Major surgical procedure or significant traumatic injury within 28 days before the first dose of study drug or anticipation of the need for major surgery during the course of study treatment.
- 3. Any unresolved toxicity (National Cancer Institute Common Terminology Criteria for Adverse Event [CTCAE] version 4.03 [v4.03]) Grade 2 or greater from previous anticancer therapy with the exception of alopecia, and the laboratory values defined in the inclusion criterion 8. Hearing loss of Grade 3 or lower and peripheral neuropathy of Grade 2 or lower is allowed. Subjects with Grade ≥ 2 neuropathy will be evaluated on a case-by-case basis after consultation with the Study Physician. Subjects with irreversible toxicity not reasonably expected to be exacerbated by treatment with durvalumab may be included only after consultation with the Study Physician.
- 4. Current or prior use of immunosuppressive medication within 14 days prior to first study dose, with the exception of intranasal and inhaled corticosteroids or systemic corticosteroids at physiologic doses not to exceed 10 mg/day of prednisone or equivalent. Steroids as premedication for hypersensitivity reactions due to radiographic contrast agents are allowed.
- 5. Patients requiring therapeutic anticoagulation and irreversible platelet inhibitors (e.g. clopidogrel, prasugrel, or ticagrelor). Low dose aspirin for cardiac prophylaxis is allowed.
- 6. History of primary immunodeficiency.
- 7. Patients who have had prior exposure to immune-mediated therapy, including but not limited to prior exposure to T-cell and natural killer cell directed therapy, anti-PD-1, anti-PD-L1, anti-CD137, and anti-CTLA4.
- 8. History of allogeneic organ transplantation.
- 9. Active or prior documented autoimmune or inflammatory disorders (including inflammatory bowel disease [e.g. colitis, ulcerative colitis or Crohn's disease], diverticulitis [with the exception of diverticulosis], systemic lupus erythematosus, Sarcoidosis syndrome, or Wegener syndrome [granulomatosis with polyangiitis, Graves' disease, rheumatoid arthritis, hypophysitis, uveitis, etc.]). The following are exceptions to this criterion:
 - Patients with vitiligo or alopecia,
 - Patients with hypothyroidism (e.g. following Hashimoto syndrome) stable on hormone replacement,
 - Any chronic skin condition that does not require systemic therapy,
 - Patients without active disease in the last 5 years may be included but only after consultation with the study physician, and
 - Patients with celiac disease controlled by diet alone.

Version Number: 1.8 Date: July 26, 2019

Proprietary of MD Anderson Cancer Center

- 10. Uncontrolled intercurrent illness, including, but not limited to, ongoing or active infection, uncontrolled hypertension, interstitial lung disease, serious chronic gastrointestinal conditions associated with diarrhea, or psychiatric illness/social situations that would limit compliance with study requirement, substantially increase risk of incurring AEs, or compromise the ability of the patient to give written informed consent.
- 11. Patients with spinal cord compression or a history of leptomeningeal carcinomatosis. At the time of Day 1 of the study, patients with central nervous system metastases must have been treated and must be asymptomatic and meet the following criteria.
 - No concurrent treatment, inclusive of, but not limited to, surgery, radiation, and/or corticosteroids. **Note:** patients are allowed on systemic steroids as detailed in Exclusion Criterion 4 unless these are being administered to manage central nervous system metastases.
 - Neurologic stability (lack of signs or symptoms greater than baseline prior to radiotherapy) until the time of dosing of MEDI0457.
 - For radiation treatment, patients must be:
 - i. At least 14 days between last day of stereotactic radiosurgery or gamma-knife treatment and Day 1 of protocol treatment,
 - ii. At least 28 days between last day of whole brain radiation therapy and Day 1 of protocol treatment, and/or
 - iii. At least 14 days since last dose of corticosteroids and Day 1 of protocol treatment.
- 12. Patients with cardiovascular (CV) disease conditions including New York Heart Association Class 3 or 4 congestive heart failure, unstable angina pectoris, or clinically important cardiac arrhythmias OR a recent (< 3 months) CV event, including myocardial infarction, unstable angina pectoris, or stroke.
- 13. Mean QT interval corrected for heart rate (QTc) ≥ 470 ms calculated from ECG using Fridericia's Correction by manual read.
- 14. Active tuberculosis (clinical evaluation that includes clinical history, physical examination and radiographic findings, and tuberculosis testing in line with local practice) infection.
- 15. Presence of acute or chronic hepatitis B (HBV) or active hepatitis C (HCV). Patients with a past or resolved HBV infection (defined as the presence of hepatitis B core antibody [anti-HBc] and absence of HBsAg) are eligible. Patients positive for HCV antibody are eligible only if polymerase chain reaction is negative for HCV RNA.
- 16. Receipt of live, attenuated vaccine within 30 days prior to the first dose of MEDI0457.

 Note: Patients, if enrolled, should not receive live vaccine during the study and up to 30 days after the last dose of IP.
- 17. Other untreated coexisting HIV related malignancies.
- 18. History of another primary malignancy except for:

Version Number: 1.8 Date: July 26, 2019 Proprietary of MD Anderson Cancer Center

- malignancy treated with curative intent and with no known active disease ≥ 2 years before the first dose of IP and of low potential risk for recurrence,
- adequately treated non-melanoma skin cancer or lentigo maligna without evidence of disease, or
- adequately treated carcinoma in situ without evidence of disease.
- 19. Pregnant or breastfeeding female patients.
- 20. Known allergy or hypersensitivity to study treatment or any of the study drugs excipients.
- 21. Any medical condition that, in the opinion of the investigator, would interfere with evaluation of the study treatment or interpretation of patient safety or study results.
- 22. Patients with active or prior digestive tract bleeding.
- 23. Patients with uncontrolled seizures.
- 24. Fewer than two acceptable sites exist for IM injection and EP between the deltoid and lateral quadriceps muscles. **Note:** A site for injection/EP is not acceptable if there are tattoos or scars within 2 cm of the proposed injection/EP site or if there is implanted metal within the same limb. Any device implanted in the chest (e.g. cardiac pacemaker or defibrillator) excludes the use of the deltoid muscle on the same side of the body.
- 25. Patients who are unable to provide informed consent, are incarcerated, or are unable to follow protocol requirements.

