- Serum Chemistry panel includes: albumin, alkaline phosphatase, ALT, AST, bicarbonate, calcium, chloride, glucose, lactate dehydrogenase, magnesium, potassium, sodium, total bilirubin (if Total bilirubin is $\ge 2x$ ULN [and no evidence of Gilbert's syndrome] then fractionate into direct and indirect bilirubin), total protein, creatinine, creatinine phosphokinase, blood urea nitrogen, uric acid, amylase and lipase. Please note: GGT to be collected at baseline and as clinically indicated.
- ^s Prothrombin time, APTT and INR.
- Free triiodothyronine (T₃) and free thyroxine (T₄) will only be measured if TSH is abnormal. They should also be measured if there is clinical suspicion of an AE related to the endocrine system.
- ^u Urinalysis panel includes: bilirubin, blood, glucose, ketones, pH, protein, specific gravity, and color/appearance.
- ^v Only for women of childbearing potential.
- To include luteinizing hormone and follicle-stimulating hormone only for women of child bearing potential who may be post-menopausal.
- x Patients with a negative serum pregnancy test within 3 days prior to Day 1 do not require a Week 1 Day 1 pregnancy test to be performed.
- y A window of ±3 days for all time points except C1D1. For Cycles 1 and 2, an interval of 7 days must occur between MEDI0457 and durvalumab treatments.
- ² MEDI0457 post-treatment reactions will be assessed 30 to 60 min after study treatment.
- ^{aa} A window of ± 3 days applies to all time points.
- bb Core tumor biopsies will be collected as per **Section 6.6.1**.
- cc ± 3 days. Biopsies at this time point are required until 10 subjects have provided tissue and then are optional for all subsequent subjects.
- dd At time of confirmed disease progression; Optional
- ^{ee} See **Section 6.6.2.1** for HPV Serology Research Blood details.
- ff Week 16 and then every 8 weeks until end of treatment.
- gg See Section 6.6.2.2 for Pharmacokinetics/ADA details.
- hh Week 16 only.
- ii For HIV(+) patients, viral load will be drawn at baseline, every month for the first 3 months, then every 3 months thereafter while on therapy.
- ^{jj} For patients with inactive Hepatitis B (Hep B core Ab(+)/HepB sAg (-)), HBV DNA and Hep BsAg will be monitored every month for the first 3 months, then every 3 months thereafter while on therapy.

Version Number: 1.8 Date: July 26, 2019 Proprietary of MD Anderson Cancer Center

STUDY ASSESSMENTS 6.

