7.6.4. Hepatic Function Abnormality

Hepatic function abnormality (i.e., TBL, ALT, or AST outside of the levels defined in the inclusion criteria) in a study patient, with or without associated clinical manifestations, is required to be reported as "hepatic function abnormal" within 24 hours of knowledge of the event to the MDACC IND Office and supporting companies or designee unless a definitive underlying diagnosis for the abnormality (e.g., cholelithiasis or bile duct obstruction) that is unrelated to IP has been confirmed.

If the definitive underlying diagnosis for the abnormality has been established and is unrelated to IP, the decision to continue administration of the study patient will be based on the clinical judgment of the investigator.

If no definitive underlying diagnosis for the abnormality is established, administration of IP to the study patient must be interrupted immediately. Follow-up investigations and inquiries must be initiated by the investigational site without delay. Each reported event of hepatic function abnormality will be followed by the investigator and evaluated by the supporting companies.

Version Number: 1.8 Date: Inly 26, 2019 Proprietary of MD Anderson Cancer Center

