During the course of the study the investigator will remain vigilant for increases in liver biochemistry. The investigator is responsible for determining whether a patient meets potential Hy's Law (PHL) criteria at any point during the study.

The investigator participates in review and assessment of cases meeting PHL criteria to agree whether Hy's Law (HL) criteria are met. Hy's Law criteria are met if there is no alternative explanation for the elevations in liver biochemistry other than Drug Induced Liver Injury (DILI) caused by the IP.

The investigator is responsible for recording data pertaining to PHL/HL cases and for reporting adverse events (AEs) and serious adverse events (SAEs) according to the outcome of the review and assessment in line with standard safety reporting processes.

Definitions

Potential Hy's Law

A PHL case is defined as a study patient with an increase in serum aspartate aminotransferase (AST) or alanine aminotransferase (ALT) ≥ 3 x upper limit of normal (ULN) together with total bilirubin (TBL) ≥ 2 x ULN, irrespective of an increase in alkaline phosphatase (ALP), at any point during the study following the start of study medication.

Hy's Law

A HL case is defined as a study patient with an increase in serum AST or ALT \geq 3 x ULN together with TBL ≥ 2 x ULN, where no other reason, other than the IP, can be found to explain the combination of increases, e.g., elevated ALP indicating cholestasis, viral hepatitis, another drug.

For PHL and HL, the elevation in transaminases must precede or be coincident with (i.e., on the same day) the elevation in TBL, but there is no specified timeframe within which the elevations in transaminases and TBL must occur.

Identification of Potential Hy's Law Cases

In order to identify cases of PHL, it is important to perform a comprehensive review of laboratory data for any patient who meets any of the following identification criteria in isolation or in combination:

 $ALT \ge 3 \times ULN$

 $AST \ge 3 \times ULN$

Version Number: 1.8 Date: July 26, 2019 Proprietary of MD Anderson Cancer Center

 $TBL > 2 \times ULN$

When a patient meets any of the identification criteria, in isolation or in combination, the central laboratory will immediately send an alert to the investigator.

The investigator will also remain vigilant for any local laboratory reports where the identification criteria are met, where this is the case the investigator will:

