function tests [LFTs]) Infliximab should not be used for management of immune-related hepatitis	elevation (CTCAE version 4.03) Any grade Grade 1 (AST or ALT > upper limit of normal [ULN] to 3 times ULN and/or TBL > ULN to 1.5 times ULN)	No dose modification. If it worsens, treat as Grade 2 event.	 alkaline phosphatase (ALP), and total bilirubin (TBL) Evaluate for alternative etiologies (e.g., viral hepatitis, disease progression, concomitant medications). For Grade 1 AST or ALT and/or TBL elevation Continue LFT monitoring per protocol.
	Grade 2 (AST or ALT > 3 to 5 times ULN and/or TBL > 1.5-3.0 times ULN)	 Hold study drug/study regimen dose until Grade 2 resolution to ≤ Grade 1 If toxicity worsens then treat as Grade 3 or Grade 4 Study drug/study treatment can be resumed based upon treating physician's clinical judgment at the next scheduled dose once event stabilizes to Grade ≤ 1 or baseline and 5-7 days have passed after completion of steroid taper. 	 For Grade 2 AST or ALT and or TBL elevation: Regular and frequent checking of LFTs (e.g., every 1-2 days) until elevations of these are improving or resolved. If no resolution to ≤ Grade 1 in 1-2 days, discuss with Study Physician. If event is persistent (> 3-5 days) or worsens, promptly start prednisone 1-2 mg/kg/day or IV equivalent. If still no improvement within 3-5 days despite 1-2 mg/kg/day of prednisone or IV equivalent, consider additional work-up and prompt treatment with IV methylprednisolone 2-4 mg/kg/day started. If still no improvement within 3-5 days despite 2-4 mg/kg/day of IV methylprednisolone, promptly start immunosuppressives (mycophenolate mofetil)⁴. Discuss with Study Physician if mycophenolate mofetil is not available. Infliximab should NOT be used. Once improving, gradually taper steroids over ≥ 28 days and consider prophylactic antibiotics, antifungals and anti PCP treatment (please refer to current NCCN guidelines for treatment of cancer-related infections [Category 2B recommendation]).
	Grade 3 (AST or ALT > 5-20 times ULN and/or TBL > 3.0-10 times ULN	 For elevations in transaminases ≤ 8 × ULN, or elevations in bilirubin ≤ 5 × ULN Hold study drug/study regimen dose until resolution to ≤ Grade 1 or baseline 	 For Grade 3 or 4 AST or ALT and/or TBL elevation: Promptly initiate empiric IV methylprednisolone at 1 to 4 mg/kg/day or equivalent. If still no improvement within 3-5 days despite 1 to 4 mg/kg/day methylprednisolone IV or equivalent,

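### As printed, the Gilbert's syndrome exception in criterion 8d has no upper bilirubin limit; read literally, it admits patients above 3 × ULN and refuses those between 1.5 and 3 × ULN

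*Combined protocol and SAP*

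**What the plan says.** Section 3.1, criterion 8, is introduced as "Adequate organ and bone marrow function within 28 days of Day 0". Its two liver items are:

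- 8d: "Total bilirubin (TBL) $\leq 1.5 \times \text{upper limit of normal (ULN"), followed by "except patients with documented Gilbert's syndrome ($> 3 \times ULN").
- 8e: "Alanine aminotransferase (ALT) and aspartate aminotransferase (AST) $\leq 3 \times ULN".

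Gilbert's syndrome appears in only one other place, the serum chemistry note to Table 3. When TBL is at least 2 × ULN, that note asks for fractionation if there is "and no evidence of Gilbert's syndrome] then fractionate into direct and indirect bilirubin". It sets no eligibility limit.

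Four other places use bilirubin thresholds, none with a provision for Gilbert's syndrome:

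- Section 7.6.4 takes its trigger from the entry criteria: "Hepatic function abnormality (i.e., TBL, ALT, or AST outside of the levels defined in the inclusion criteria").
- Section 6.7.2, DLT item i, uses TBL above 5 × ULN.
- Appendix D, Table 7, defines Grade 3 as "TBL > 3.0-10 times ULN" and discontinues study drug when bilirubin exceeds 5 × ULN.
- Appendix B defines a potential Hy's Law case by a transaminase rise "together with total bilirubin (TBL) ≥ 2 x ULN, irrespective of an increase in alkaline phosphatase".

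**The concern.** An exception to an upper limit normally gives the exempt group a higher upper limit. This one carries a greater-than sign, so it reads as a lower limit and no ceiling is stated. Sites could reasonably apply it in different ways, although Section 3 makes meeting every criterion a condition of treatment.

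Two things are at stake. The first is who enters: under the literal reading, mildly raised bilirubin from a documented cause is refused and a higher value is accepted. The second is how hepatic safety is read. Section 1.3.1 calls this the first study of the combination in these patients, and Section 7.5 lists hepatotoxicity as an adverse event of special interest. A patient admitted with high bilirubin starts treatment at or beyond thresholds that the protocol uses to hold or stop drug, and it does not consistently say whether those thresholds then refer to the patient's own baseline.

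**Working it through.** No sample size, power or error rate depends on this point, so the check is a logical one.

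**Step 1. Eligibility of a patient with documented Gilbert's syndrome, by baseline TBL.**

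| TBL (× ULN) | Literal: parenthesis defines the exempt group | Descriptive: all Gilbert's patients exempt | Parenthesis marks those not exempt |
|---|---|---|---|
| up to 1.5 | eligible | eligible | eligible |
| above 1.5 to 3 | not eligible | eligible | eligible |
| above 3 | eligible, no ceiling | eligible, no ceiling | not eligible |

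The third column of outcomes would make sense clinically, but the words do not say it. The other two are the natural readings, and both lack a ceiling. Under the literal one, eligibility is non-monotone: yes, no, then yes again as bilirubin rises.

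**Step 2. Direction of the other limits in criterion 8.** Hemoglobin, neutrophils, platelets, creatinine clearance and CD4 count have lower limits. TBL, ALT/AST, serum creatinine and HIV viral load have upper limits. Each points towards better function or control. The Gilbert's parenthesis alone points the other way.

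**Step 3. Is there a ceiling elsewhere?** The exclusion criteria set no bilirubin limit. Exclusion 3 concerns unresolved toxicity of earlier anticancer therapy, and it exempts the laboratory values in criterion 8. Exclusion 21 lets the investigator exclude a condition that would interfere with interpretation, but this is discretionary and gives no value.

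**Step 4. Where an admitted patient falls under the on-study rules.**

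| Baseline TBL (× ULN) | Table 7 bilirubin band | Table 7 action | DLT item i (above 5) |
|---|---|---|---|
| above 1.5 to 3.0 | Grade 2 | hold | below |
| above 3.0 to 5 | Grade 3 | hold | below |
| above 5 to 10 | Grade 3 | discontinue | above |
| above 10 | Grade 4 | permanently discontinue | above |

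Every patient in the literal exempt group (above 3 × ULN) therefore starts in the Grade 3 band or higher. Anyone above 5 × ULN starts beyond the discontinuation level.

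**Step 5. Baseline or ULN?** Table 7 lets dosing resume at Grade 1 or below, or at baseline. Its Grade 3 entry also discontinues permanently if elevations do not fall to Grade 1 or below, and there it gives no baseline alternative. Grade 1 ends at 1.5 × ULN, and only patients above 1.5 × ULN need the exception. A patient who used the exception therefore cannot reach Grade 1 by returning to baseline, and the two lines conflict for that patient.

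**Step 6. Section 7.6.4.** Its trigger is a value outside the inclusion levels. For these patients the inclusion levels are either the broken set in the literal column of Step 1 or no limit at all, so the trigger has no defined upper edge.

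**The case against.** The strongest reply has three parts.

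First, everything rests on one sign. Comparison signs look unreliable elsewhere in the available text: note a to Table 2 gives a failure rate equal to 1% where an inequality is expected. That justifies a check against the source document. However, that slip loses part of a symbol rather than reversing it, and the upper-bound sign in the same line of 8d is intact. A reversed sign is therefore the best inference, not an established fact.

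Second, the parenthesis may be merely descriptive, in which case nobody between 1.5 and 3 × ULN is refused. This stands as a possible reading, but it does not supply a ceiling.

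Third, the safety rules contain protections, and these answer several stronger conclusions that a reader might draw:

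- *A raised baseline would count as a DLT, and so as one of the four that stop a cohort at 4/6.* Section 6.7.2 confines DLTs to treatment-related toxicity arising in the evaluation period. Section 7.3.2 treats an event that preceded the product, or has a clearly more likely explanation, as unrelated. An unchanged baseline value is not a DLT.
- *Such a patient already meets half of Potential Hy's Law.* Appendix B requires an increase after study medication starts, with the transaminase rise first or on the same day. A long-standing bilirubin elevation does not fit that order. How the definition applies to these patients is unclear, and the section on criteria met before treatment covers only patients with liver metastases.
- *Section 7.6.4 would fire when bilirubin falls.* A value of 1.5 × ULN or below meets the general limit, so at most the 1.5 to 3 band is affected, and only under the literal reading. The section also waives the report when an unrelated definitive diagnosis is confirmed, which documented Gilbert's syndrome may be.
- *Hepatic events could not be attributed at all.* Table 7 requires a search for other causes, and Section 6.7.1 requires no dose modification for events clearly not attributable to durvalumab.

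These protections reduce the consequences. They do not repair the entry rule.

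**Conclusion.** The point holds in a limited form. As printed, criterion 8d gives no upper bilirubin limit for patients with documented Gilbert's syndrome under either natural reading. Under the literal one it accepts higher values while refusing moderate ones. It conflicts with the purpose of criterion 8 and with the thresholds in Table 7, and it leaves the Section 7.6.4 trigger undefined for these patients.

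The size is small. The documents give no count of patients with Gilbert's syndrome or of their bilirubin values, but few are likely to be affected. The response boundaries and power of the two-stage design do not change, and attribution rules would avert many false DLT, reporting or Hy's Law signals. The conclusion assumes that the sign in the source document matches the available text. That it points the wrong way is an inference, because the intended limit is nowhere stated.

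A reader might go further and ask that nobody enter already meeting a hold threshold. The documents do not support that. The Table 7 hold begins just above 1.5 × ULN, exactly where the general limit ends, so such a requirement would abolish the exception and settle a clinical limit that belongs to the sponsor.

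**What to change.** 1. Check the sign in 8d against the source document.
2. Restate 8d so that the direction and limit of the Gilbert's exception are explicit, with the value set by the sponsor.
3. Reconcile 8d with Section 7.6.4, DLT item i, Table 7 and Appendix B by stating, for these patients, whether each bilirubin threshold refers to baseline or to ULN. Include the two Table 7 lines that differ on whether a return to baseline is enough.
4. If any patient has already entered under the exception, list baseline TBL and the reading that the site applied.

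The cost is a short wording amendment with cross-references. No new tests are needed, because bilirubin is already in the Table 3 chemistry panel. The effect on accrual should be very small.
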